We will analyze and compare cancer serum peptidomes using two different mass spectrometry platforms, MALDI-TOF and LC-MS (MS/MS), each at two different locations, the [name] Lab at MSKCC and the [name] Lab at New York University (NYU); i.e., the *NY consortium*. Four standalone instruments will therefore be used in the work described in this proposal. Systematic performance and reproducibility comparisons will be carried out between the two instruments of platform and between the two platforms.

Serum peptide samples are prepared for MALDI-TOF MS analysis using an automated liquid handling system, to form a fully integrated and previously optimized platform (Appendix A). A mirror robot/MALDI platform is established at NYU, with identical liquid handler but from a different manufacturer. Conversely, a capillary liquid chromatography (cLC) system coupled to an electrospray (ESI) hybrid quadrupole (Q)-TOF mass spectrometer will first be tested and optimized for serum peptidome analysis at NYU, and then accurately copied at MSKCC using a cLC system and Q-TOF mass spectrometer from different manufacturers.

IRB
PB

Amended: 2/1/12

Memorial Sloan-Kettering Cancer Center IRB Protocol

IRB#: 08-114 A(4)

While in general the throughput of LC-MS is lower than that of MALDI-TOF, we feel that it will be very useful to use LC-MS to evaluate the biomarker discovery platform using MALDI-TOF. We anticipate that LC-MS based peptide quantitation should provide greater depth of coverage of the peptidome than MALDI-TOF because of the extra dimension of analysis provided by separating proteins into subgroups direct coupling of HPLC to the mass spectrometer. In addition, LC-MS will enable rapid identification by MS/MS of peptides of interest- i.e., those that have diagnostic value for differentiating between disease and control groups. The [name] lab has extensive experience in using nanoflow HPLC-Q-TOF LC-MS/MS for the identification and relative quantification of proteins and peptides.

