11.0 BIOSTATISTICS

This is a prospective, serum proteomics study of men who are to undergo prostate biopsy. The purpose is to determine if proteomic profiles can be used to distinguish between men with prostate cancer on biopsy from men with no cancer on biopsy. Overall, 500 men will be part of the study. Based on previous experience, about 30% (150 patients) will have cancer and about 70% (350 patients) will not. Accrual is expected to take two years.

An initial biopsy will be undertaken for these patients because of a suspicion of prostate cancer. Because there is about a 20% false negative rate on a single biopsy, and a negligible false positive rate, a second biopsy will be recommended at six months only for those who are negative on the first biopsy. Patients who are positive on the first or second biopsy will be assigned to the “cancer” group, while those who are negative for all their biopsies will be assigned to the “no cancer” group. Assuming the two biopsies can be treated as independent, there would be about 4% that should be in the “cancer” group that would be assigned to the “no cancer” group if all those negative on the first biopsy got the second biopsy. We believe that over 90% of the patients that are negative on the first biopsy will get the second biopsy, leading to an expected false negative rate of 5 to 6%. Since the number incorrectly assigned should be small, we ignore it in the calculations below.

The data from each proteomic study is a two-dimensional plot of mass over charge (m/z) and intensity. The intensity at a particular m/z is proportional to the amount of the peptide with that particular molecular weight in the sample. The m/z values are continuous, but as a first step, these values will be reduced to a finite set of “bins” based on intensity “peaks” across samples, as previously described.¹² To prevent against bias, the bins and the intensities at each bin will be computed while blinded to disease status. The value for each m/z bin for each

**IRB
PB**

Amended: 2/1/12

Memorial Sloan-Kettering Cancer Center IRB Protocol

IRB#: 08-114 A(4)

sample will be analyzed in two ways. One way will be to use the actual intensity measure, while the other way will be to convert it to a binary (absence or presence) value.

Primary Objectives:

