Sample size considerations for the prediction rules are based on the AUC. The methods used here were introduced by Pepe.¹⁸ Since the known biomarkers, such as PSA, give an AUC of approximately 0.8, our goal in Aim 1 is a prediction rule with an AUC of greater than 0.8. For the validation set of size 250, fixing the type I error rate at 0.05, the true AUC would have to be at least 0.86 to have at least 80% power. This is based on a one sample test. In Aim 2, we are comparing the AUC of combining the standard biomarkers with proteomic data to just using the biomarkers. In this case, the AUC of the biomarkers plus proteomic model would have to be at least 0.89 to have at least 80% power. This is a two sample test. While the data are paired, we follow Pepe’s recommendation¹⁸ to treat the samples as independent for sample size determination because the correlation is unknown without pilot data and treating the samples as independent is conservative.

In addition to prediction, the association between peak intensity and group membership (“cancer” vs. “no cancer”) will be evaluated for every bin using the Wilcoxon rank sum test or Fisher’s exact test, depending on whether the data is being treated as continuous or binary. Adjustment will be made for multiple comparisons using the false discovery rate methods of Benjamini and Hochberg.¹⁹ Finally, the data will be hierarchically clustered to examine whether there are distinct peptide patterns associated with subsets of samples.

IRB
PB

Amended: 2/1/12

Memorial Sloan-Kettering Cancer Center IRB Protocol

IRB#: 08-114 A(4)

The full set of 500 samples will be examined using the standard MALDI technique at MSKCC. Thus, the main prediction rules that will be reported will be for these samples using this method at this site. As there are three time points, three separate rules will need to be reported and compared as discussed below. In addition, all data sets will be simultaneously processed in order to get the same sets of bins for reproducibility comparisons. Two other MALDI methods and two LC-MS methods will be used on a subset. For each, the same subset of 100 malignant samples and 100 benign samples will be examined. The same analyses as on the full set will be undertaken, but here 50 of each will be used as a training set and 50 of each will be used as a test set.

Secondary Objectives:

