The proteomic profiles of Caucasian men and of African-American men will be compared to see if the same peaks that are predictive in one are predictive in the other. In addition, the AUCs for the two groups will be compared based on models that use all the data.²⁰ Finally, separate models will be built for the two groups and the AUCs will again be compared.

As mentioned in section 4, we distinguish two aspects of reproducibility: *analytical* reproducibility, that is, whether a proteomics machine produces similar peaks on repeated samples, and *inferential* reproducibility, whether a proteomics experiment produces similar conclusions when repeated.

The basic method for assessing analytic reproducibility will be through the concordance correlation coefficient (CCC)²¹ of the intensity estimates. This CCC is a measure of the agreement between two readings of the same sample via the variation from the 45 degree line through the origin. It is on the same -1 to 1 scale as the standard Pearson correlation. Since there are about 600 bins per sample, there will be 600 CCCs for every comparison. Therefore, we will compute summary statistics of the CCCs. These summaries will be based on all the bins and just the discriminating bins. Since the statistic is only pair-wise, different analyses will have to be done for the three time points, the two sites, and the two platforms (MALDI and LC-MS). The only comparison between the platforms will be between standard MALDI and standard LC-MS.

Inferential reproducibility will consist of two components: determination of whether the same peaks are discriminating and comparisons of the AUCs for the prediction of cancer or no cancer. These comparisons will be made for the same varying conditions as for analytic reproducibility. For the former, discriminating peaks will be identified using a variety of thresholds and the differences will be reported as summary statistics. For the latter, formal testing of differences in AUCs will be undertaken, as well as summary statistics. A question of particular interest will be whether the difference in the estimated AUC from the two sites using the standard MALDI platform is statistically significant.

IRB
PB

Amended: 2/1/12

Memorial Sloan-Kettering Cancer Center IRB Protocol

IRB#: 08-114 A(4)

The last two secondary aims involve collection of material for future studies and no current data analyses.

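### As written, a shared m/z bin need not hold the same peptide on MALDI and LC-MS, so weak bin-wise agreement between the platforms could come from the binning

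*Combined protocol and SAP*

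**What the plan says.** Section 11.0 opens with one description for all the proteomic data: "The data from each proteomic study is a two-dimensional plot of mass over charge (m/z) and intensity". It goes on to give an m/z value the meaning of a molecular weight: "The intensity at a particular m/z is proportional to the amount of the peptide with that particular molecular weight in the sample". The m/z axis is then cut into bins by a published method (reference 12), blinded to disease status.

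Under Primary Objectives, the same section says that "all data sets will be simultaneously processed in order to get the same sets of bins for reproducibility comparisons".

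Under Secondary Objectives, analytical reproducibility is measured by a CCC for each bin. With about 600 bins, this gives 600 CCCs for each comparison, and the comparisons named are time points, sites and platforms. On platforms the text adds: "The only comparison between the platforms will be between standard MALDI and standard LC-MS". Inferential reproducibility covers the same conditions and has two parts: which peaks discriminate, and how the AUCs compare.

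Section 4.2 describes the LC-MS instrument as "a capillary liquid chromatography (cLC) system coupled to an electrospray (ESI) hybrid quadrupole (Q)-TOF mass spectrometer". It expects greater depth of coverage than MALDI from "the extra dimension of analysis provided by separating proteins into subgroups direct coupling of HPLC to the mass spectrometer".

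**The concern.** A CCC measures agreement between two readings of the same quantity, and overlap of discriminating peaks means something only if a peak has the same identity on both sides. The plan secures this by giving all data sets the same bins. That works when the instruments place a given peptide at the same m/z. Section 4.2 gives two reasons why MALDI and LC-MS might not: a different ion source, which can give a different charge, and a separation dimension that an m/z bin does not carry.

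No section describes conversion of LC-MS signals to neutral mass, handling of retention time, or a rule for linking features across platforms. The binning method cited is the one that section 4.2 ties to the sponsor's MALDI work. That section also says that intensity-based LC-MS profiling had so far not been applied to the serum peptidome.

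At stake is the platform part of the reproducibility objective in section 2.2. Section 4.2 gives evaluation of the MALDI discovery platform as a use of LC-MS and plans 400 standard LC-MS analyses at each site. If bin-wise agreement turned out low, a reader could not tell an instrument problem from a pairing problem.

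**Working it through.** **Inputs**
- From the documents: common bins for the reproducibility comparisons, data treated as m/z by intensity, and about 600 bins (section 11.0); electrospray source and chromatographic separation (section 4.2); the same 100 malignant and 100 benign samples, 200 in all, for the subset methods (sections 4.2 and 11.0).
- Not in the documents: charge states. Assumption: MALDI ions mainly at charge 1, which is also what reading m/z as molecular weight implies; electrospray ions at charge 1, 2 or 3. The proton mass, 1.00728 Da, is a physical constant.

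**Step 1. The plan's own figure.** One CCC per bin × about 600 bins = about 600 CCCs per comparison, as stated. For the platform pair this count requires each bin to exist, and to mean the same thing, on both platforms.

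**Step 2. Where a peptide of mass M lies at charge z.** m/z = (M + 1.00728 z) / z.

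| M (Da) | z = 1 | z = 2 | z = 3 |
|---|---|---|---|
| 1,000 | 1001.01 | 501.01 | 334.34 |
| 2,000 | 2001.01 | 1001.01 | 667.67 |
| 3,000 | 3001.01 | 1501.01 | 1001.01 |

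For example, (2,000 + 2 × 1.00728) / 2 = 2,002.01456 / 2 = 1001.01.

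**Step 3. One bin on two platforms.** The bin near m/z 1001 holds a 1,000 Da peptide at charge 1, a 2,000 Da peptide at charge 2 and a 3,000 Da peptide at charge 3. Under the assumption, a CCC in that bin could set the MALDI intensity of the first against the electrospray intensity of the other two.

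**Step 4. Elution time.** Reducing LC-MS to m/z and intensity adds together peptides that the column had separated. Where charges differ, peptides of different mass enter the same sum. Where every ion is at charge 1, only peptides of about the same mass are pooled. The masses then line up with MALDI, but the extra dimension goes unused.

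**Step 5. Range.** Let f be the share of peptides that electrospray shows only at charge 2 or more. At f = 0 no bin is mismatched by charge. At f = 1 no peptide lies in its own MALDI bin. The documents give nothing that narrows f.

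**Step 6. Which analyses need matched bins.**

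| Analysis | Needs bins matched across platforms? |
|---|---|
| CCC, MALDI versus LC-MS | Yes |
| Overlap of discriminating peaks, MALDI versus LC-MS | Yes |
| AUC comparison, MALDI versus LC-MS | No; each rule uses its own features |
| Run-to-run and site-to-site comparisons within a platform | No |
| Main prediction rules, standard MALDI at MSKCC | No |

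**The case against.** The strongest reply is that this is an unstated processing step and not an error. The sentence on common bins follows the text on three MALDI time points and precedes the sentence that introduces the LC-MS methods, so it could be meant for MALDI only. The opening description of the data is generic, and its reference to molecular weight would suit a mass axis after charge deconvolution. Section 4.2 says the LC-MS system was still to be tested and optimised for the serum peptidome, so its data processing may have been left for later.

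Part of this stands. The plan nowhere says that retention time is discarded or that deconvolution is omitted, so the fair statement is that a bin need not refer to the same peptide, not that it never does. But the MALDI-only reading does not close the gap. The Secondary Objectives still call for bin-wise CCCs between platforms, and on that reading no rule pairs the features at all.

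The reply is also right about several stronger inferences a reader might draw:
- **Agreement near zero, or overlap at chance level.** Neither a CCC nor an overlap has been estimated here. Ions at charge 1 would still align, and the loss depends on an unknown share.
- **Failure of the whole platform comparison.** The AUC component needs no matched bins, and it is the component with formal testing. The CCCs and peak overlap are reported as summary statistics.
- **LC-MS prediction rules stripped of their resolution.** The common-bin sentence is limited to reproducibility comparisons and does not fix how LC-MS features are formed for modelling.
- **MS/MS able to link every feature.** Section 4.2 describes MS/MS identification for peptides of diagnostic interest only.

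**Conclusion.** The point holds in limited form. Followed as written, section 11.0 pairs MALDI and LC-MS readings by m/z alone, while section 4.2 describes an LC-MS system for which m/z alone does not identify a peptide. Low cross-platform CCCs or few shared discriminating peaks could therefore be produced by the binning, and could not be read as evidence about either instrument.

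The size cannot be fixed from the documents. It rests on the assumption that some electrospray ions are multiply charged and on no deconvolution being applied, and the charge mismatch could range from none of the bins to all of them. The effect is confined to the two bin-wise summaries within one secondary objective. The site comparison on standard MALDI, which the plan singles out as of particular interest, is among the analyses left untouched. The plan should be changed before the LC-MS data are processed, but nothing here undermines the primary objectives.

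**What to change.** Amend section 11.0 as follows:

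1. Keep common m/z bins for same-platform comparisons only (run versus run, site versus site).
2. For the cross-platform work, define LC-MS features by retention time and charge-deconvoluted neutral mass.
3. Link MALDI and LC-MS features by neutral mass within a tolerance stated in advance, with the linking done blinded to disease status, as the plan already requires for the bins. Use MS/MS identity to confirm links where it is available for peptides of interest.
4. Restrict the cross-platform CCC and peak-overlap summaries to linked peptides in the same 200 samples, and report how many were linked.

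The cost is SAP wording and some extra data processing on runs already planned; no further patients or blood draws are needed. The downside is that fewer than about 600 features enter the cross-platform comparison, so its summaries describe the linked peptides and not the whole spectrum.

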1.0 PROTOCOL SUMMARY AND/OR SCHEMA

Current recommendations suggest that all men over the age of 50 years should have annual prostate cancer screening with serum PSA measurement and digital rectal examination. Men with an abnormal examination and/or an elevated PSA test are generally referred for a prostate biopsy. Not all men with an elevated PSA have prostate cancer. Positive biopsy rates in a screened population will be in the order of 25-40%.^{1,2} A recent study demonstrated a positive prostate biopsy rate for African American men with an elevated PSA and/or abnormal DRE to be 33%.³

Incidence rates of prostate cancer for African-Americans are among the highest in the world. Men of African descent have a 60 percent higher risk of developing prostate cancer than Caucasian men and have twice the risk of dying from it.⁴ Furthermore, African American men have higher levels of testosterone, which may contribute to higher serum PSA levels, worse Gleason scores, and more advanced stage of disease at diagnosis. The increased risk of advanced stage disease persists in African-American men, even after adjustment for socioeconomic, educational, and clinical variables. The patient population of SUNY Downstate Medical Center, Brooklyn offers a unique opportunity to recruit a large number of African-American men. The patient population at New York Presbyterian Hospital, Weill Medical College of Cornell University, Manhattan offers the opportunity to recruit a large Caucasian population. The patient population attending MSKCC predominately have a diagnosis of prostate cancer already on their first attendance and hence are unsuitable for this study.

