2.2 Secondary Objectives

- To determine if Caucasian men and men of African-American descent with and without prostate cancer have different proteomic profiles.
- To assess reproducibility of proteomic profiles over different runs, platforms, and sites.
- To procure a DNA repository from these patients undergoing prostate biopsy for future assessment of kallikrein gene expression.
- To establish a bank of DNA, serum, and frozen lymphoblastoid cells from these patients for the purpose of enabling genetic investigations in men with a diagnosis of prostate cancer.

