4.0 OVERVIEW OF STUDY DESIGN/INTERVENTION

4.1 Design

This study will enroll two groups of 250 patients who are to undergo prostatic biopsy as part of their routine medical care because of suspicion of prostate cancer (elevated PSA between 2 and 10 ng/ml, abnormal rectal examination, or both). The first group will contain 250 patients of African-American descent and the second will contain 250 Caucasian men. The patients (both African American and Caucasian) will be recruited at both centres - New York Presbyterian Hospital, Weill Medical College of Cornell University, Manhattan and SUNY Downstate Medical Center in Brooklyn.

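### The peak-level race analysis checks whether predictive peaks carry over between races but never tests or estimates the difference in cancer effect; separately, no analysis names enrolling hospital

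*Combined protocol and SAP*

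**What the plan says.** Section 2.2 sets the objective: "To determine if Caucasian men and men of African-American descent with and without prostate cancer have different proteomic profiles". Section 11.0 (Secondary Objectives) answers it in three ways.

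- **Peaks:** profiles of the two races are "compared to see if the same peaks that are predictive in one are predictive in the other". No test, threshold, estimate or interval is given.
- **AUC from common models:** "the AUCs for the two groups will be compared based on models that use all the data".
- **AUC from separate models:** one set is built in each race and the AUCs are compared again.

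The per-bin tests in Section 11.0 (Wilcoxon or Fisher, "depending on whether the data is being treated as continuous or binary", with Benjamini-Hochberg adjustment) compare cancer with no cancer. They have no race term, and no false-discovery level is stated. Each bin is analysed as an intensity and also after a step to "convert it to a binary (absence or presence) value". For reproducibility, the same section is more explicit: "discriminating peaks will be identified using a variety of thresholds and the differences will be reported as summary statistics". It gives no such method for race.

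On hospital, Section 1.0 says that SUNY Downstate in "Brooklyn offers a unique opportunity to recruit a large number of African-American men" and presents Weill Cornell as the source of Caucasian men. Section 4.1 adds: "The patients (both African American and Caucasian) will be recruited at both centres". Section 4.2 says that blood processing materially changes the profile, and relies on a common procedure to keep differences between hospitals small. Section 11.0 does not name enrolling hospital. Its two sites are the assay laboratories, and its example covariates are age and family history.

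**The concern.** The peak sentence can mean two things: make a list in each race and compare the lists, or take the peaks found in one race and re-test them in the other. Neither measures the difference in cancer effect.

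A peak with the same effect in both races can miss the threshold in one of them by chance, and a peak that passes in both can have quite different effects. Readers therefore cannot tell a real race difference from low power when a peak fails to carry over, nor how similar the effects are when it does. The AUC comparisons are direct race contrasts, but they summarise whole models and cannot show which peaks differ.

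Hospital is a second, separate gap and not a cause of the chance discordance. Section 2.2 asks about profiles by race in men with and without cancer. If peak levels are compared by race to answer it, the result could partly reflect where the blood was collected and handled.

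**Working it through.** The plan gives no power, alpha or sample size for the race comparison, so there is no stated figure to reproduce.

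**Inputs from the plan**
- 250 men per race (4.1).
- Positive biopsies (6.0): 33% in African-American men, 0.33 × 250 ≈ 83 (167 without cancer); 25-30% in Caucasian men, midpoint 0.275 × 250 ≈ 69 (181 without).
- About 600 bins (11.0).

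**Assumed:** 50 true peaks of 600, identical effects in both races, Benjamini-Hochberg at 5%. Effects are in within-group SDs.

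**One peak, by hand.** Wilcoxon power ≈ Φ(d√(3/π)/SE − z). SE = √(1/83 + 1/167) = 0.134 and √(1/69 + 1/181) = 0.141. At d = 0.5:
- p < 0.001: power 0.636 and 0.565. Chance of significance in exactly one race = 0.636 × 0.435 + 0.364 × 0.565 = 0.48.
- p < 0.05: power 0.953 and 0.932. The same chance = 0.953 × 0.068 + 0.047 × 0.932 = 0.11.

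**All 600 bins, simulated (200 data sets per effect size).** "Lists" is the share of flagged peaks that are flagged in one race only. "Re-test" is the share of carried-over peaks not confirmed, with Benjamini-Hochberg 5% among those carried over and both directions pooled.

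| Identical effect (SD) | Lists | Re-test |
|---|---|---|
| 0.4 | 81% | 28% |
| 0.5 | 49% | 11% |
| 0.6 | 24% | 6% |
| 0.7 | 12% | 5% |
| 0.75 | 11% | 5% |

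About 4-5 points of each re-test figure are null bins that should fail.

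Sensitivity:
- With 20 to 100 true peaks, lists give 88-71% at 0.4 SD and 64-39% at 0.5 SD; re-test gives 27-25% and 10%.
- Correlated bins (blocks of 10, correlation 0.5) move the shares by about 4 points at most.
- Binary bins (40% presence without cancer, Fisher), odds ratios 2/2.5/3/4: lists 90/62/34/12%, re-test 43/15/7/4%.

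A Benjamini-Hochberg-adjusted interaction test flags 0.01-0.13 peaks per data set with independent bins, and up to 0.19 with correlated bins.

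**Reverse error.** If the effect is halved in one race (0.75 against 0.375 SD), 71% of carried-over peaks still pass the re-test.

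**Hospital.** Suppose a share c of one race comes from one hospital and the same share of the other race from the other. A handling shift h then creates a race difference of h(2c − 1). SE = √(1/167 + 1/181) = 0.107 without cancer and √(1/83 + 1/69) = 0.163 with cancer. Share of null bins that differ by race at a nominal 5%:

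| Assumed shift, group | c = 70% | 80% | 90% |
|---|---|---|---|
| 0.3 SD, no cancer | 20% | 39% | 61% |
| 0.3 SD, cancer | 11% | 20% | 31% |
| 0.2 SD, no cancer | 12% | 20% | 32% |

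For example, at 0.3 SD and 80% the difference is 0.3 × 0.6 = 0.18 SD, and 0.18/0.107 ≈ 1.68 standard errors gives 39%. An even split gives 5%. In linear models on all 500 men, a hospital term returns every figure to about 5%, and the interaction test stays at about 5% with or without it. In logistic models (0.5 logit shift, presence or absence), the race term in men without cancer rejects in 16/29/45% without hospital and 4-5% with it; the interaction rejects in 4-6% either way.

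**The case against.** **The re-test reading is arguably the more literal one, and under it the chance discordance is small.** This stands in part: after allowing for null bins that should fail, the problem is confined to peaks of about 0.5 SD or less. But the sentence does not choose a reading, and the re-test still passes most peaks whose effect is halved in one race.

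**The plan is silent rather than wrong, and it contrasts the races formally by AUC.** Nothing forbids reporting race-specific effects, and the AUC comparisons are real contrasts. With all 500 men, though, they need a gap of about 0.12-0.14 for 80% power (two-sided 0.05, higher AUC 0.80 or 0.86), and they do not identify peaks.

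**The interaction test would miss most real differences.** It flags only 5% of the halved effects, while separate lists show about 80% of flagged peaks as discordant in that scenario. The low power is real. But lists also show 81% when the effects are identical at 0.4 SD, so discordance does not separate the two situations. This argues for estimates with intervals.

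**The hospital point concerns an analysis not in the plan.** Section 11.0 plans no race comparison of peak level, and a pure handling shift barely affects within-race cancer comparisons or the interaction. Both races are to be enrolled at both centres under one procedure, and the covariate list is open-ended. All this stands and makes it a risk of unknown size. Still, no race-by-hospital balance is set, and Section 2.2 invites that comparison.

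**Conclusion.** The concern holds in both parts.

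1. The only peak-level answer to the race objective cannot distinguish a difference in cancer effect from chance. With identical effects, one-race-only peaks run from 81% (0.4 SD) to 11% (0.75 SD) under the list reading, and unconfirmed peaks from 28% to 5% under the re-test reading. These figures rest on the assumed number of true peaks, effect sizes and 5% false-discovery level, none of which the plan gives. The group sizes and bin count follow from the plan.
2. No analysis accounts for enrolling hospital. The size of this cannot be known without race-by-hospital counts. The 0.2-0.3 SD shift and 70-90% concordance are illustrations, and only a race comparison of peak level would be exposed.

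The objective is secondary and no primary conclusion changes. The plan should be amended because the data already collected support a better answer.

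**What to change.** In Section 11.0, Secondary Objectives:

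- Keep the peak comparison as descriptive. State the test, the false-discovery level, and whether it is a list or a re-test.
- For each bin, fit a model with cancer, race, cancer × race and enrolling hospital (three hospitals in Sections 5.0 and 6.0). Use a linear model on log or rank intensity, and a logistic model for presence or absence, Firth-penalised if a race-by-cancer cell is empty.
- Apply Benjamini-Hochberg across bins to the interaction, and separately to the race difference in men without and with cancer.
- Report race-specific effects and their difference with 95% confidence intervals. Describe an effect as differing by race only if its interaction is flagged, and do not read an unflagged or carried-over peak as equal.
- Report the race-by-hospital table.

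**Cost.** No new samples or assays are needed. Recruitment is by race (6.0) and each site registers its own participants (12.2); confirm that both fields are recorded. The work grows by three families of tests over about 600 bins, for both codings.

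**Limits to state**
- The interaction SE is √(1/83 + 1/167 + 1/69 + 1/181) = 0.195 SD, so the interval half-width is 1.96 × 0.195 = 0.38 SD.
- With 10-50 peaks having an effect in one race only, 13-25% of them are found at 0.5 SD and 66-83% at 0.75 SD. For binary bins, 16-32% are found at an odds ratio of 3 and 43-66% at 4.
- The hospital term leaves the interaction SE at 0.195. At 70/80/90% concordance it raises the race-difference SE from 0.107 to 0.114/0.127/0.160 SD without cancer, and from 0.163 to 0.167/0.176/0.202 with cancer.
- At 2% presence, 42% of bins have an empty race-by-cancer cell (4% at 5% presence), hence the penalised fit.
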